**Table 2. Theory-based Mechanisms and Measures**

Domain	Target	Theoretical	Instrument	Description	Timing
Person	Parent capacity	Improved parental attitudes about mental health increases capacity to engage in services	Parental Attitudes Towards Psychological Services Inventory	26-item questionnaire to assesses mental health attitudes and stigma	Baseline, 6, 12 months
	Parent capacity	Improved parent mental health increases capacity to engage in services	Patient Health Questionnaire-2	Validated 2-question depression screener	Baseline, 3, 6, 9, 12 months
Systems	Access to resources	Improving social determinants increases access to resources	Family Resource Scale	30 items assess adequacy of resources	Baseline, 6, 12 months
	Overcome barriers	Coordination decreases structural barriers	Electronic Health Record FP Templates	Contains resource use and care coordination activities	Monthly data reports

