## 8. Study Intervention: Family Navigation

Family navigation (FN) is care management designed to address barriers to services – in our study, behavioral health services. In this study, the core FN intervention will be delivered to all participants by study Family Partners (FP), a paraprofessional community member who is trained to support families of children with behavioral health. FN strategies to be tested will be delivered. Literature strongly supports the hypothesis that initiation of behavioral health services is directly influenced by several key domains, including: parents' motivation and capacity to pursue services (e.g., health literacy, mental health), families' resources and competing demands on their time, and healthcare system factors, such as difficulties scheduling timely appointments and barriers to communication. Core FN components (see Figure 4) are designed to address these domains. For example, motivational interviewing is included

to increased parents' motivation to pursue services. Problem-solving strategies are introduced to improve parents' capacity to pursue services, and education addresses health literacy. Assistance with social determinants of health is essential for reducing competing demands on families' time (e.g., help with housing, benefits). Care coordination is focused on healthcare system factors and is designed to promote an activated care team. The components of the core navigation intervention, which all participants will receive, are described below.

Of note, the core FN intervention exceeds the current standard of care at the health center. Dothouse

employs care managers who assist families access behavioral health services and meet concrete resource needs. However, care managers are not routinely involved with all children with behavioral health concerns and they do not support engagement longitudinally.

- Universal Screening and Behavioral Health Referral. As described above, The FN intervention begins with a family-centered response to a positive behavioral health screening or parent report of a concern. The FP will provide psychoeducation and use MI to explore family preferences regarding further evaluation, and referral to behavioral health services.

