family, they would like services and would like to work with the FP, the family will have the opportunity to enroll in the study and be randomized to a study condition. This group of parents will be called the “watchful waiting” group. The watchful waiting group will NOT be consented at the time of initial contact. If they are interested in pursuing services for their child at the time of recontact, the parent and child will be offered study participation at that time and will have the opportunity to consent to or decline participation. We have included this group based on our clinical experience. We find that many families wish to delay services for a number of reasons including life events (family moving, expecting a new baby) and timing (child going away for the summer, want services through school and school ending or not in session). We would like to make study participation available for such families.

The FP will administer the baseline assessment measures and then the family will be randomized (on an individual basis through a randomization generator centralized with the study statistician) to a study condition. If the family declines participation, the FP will refer the family to health center care managers and have no further contact with the family.

**Randomization Procedures.** Before initiation of FN, FPs will assign each family an experimental condition using a computer program. The computer program will use both a randomly-generated number and “minimization procedures” to minimize imbalances across conditions with respect to target variables, including family/child characteristics (e.g., education, gender, race/ethnicity, screening score). In this procedure, the first participant is assigned at random. Subsequent participants have a p chance of being randomly assigned and a 1-p chance of being automatically assigned to the condition that would most reduce imbalance based on selected sample characteristics. Minimization procedures are considered best practices for sequential assignment. Families with more than one child enrolled will participate in the same random condition for all children.

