### **12.2 Sample Size Determination**

#### **Sample Size and Power.**

Of the three measures to operationalize engagement, we powered our study on the dichotomous variable “receipt of BH services within 90 days” - the most conservative estimate. We base our power calculation on the number needed to detect the smallest differences in primary outcomes that are of clinical importance. Our formative work with staff at DotHouse and other community health centers indicates that a relative risk of approximately 25% would be considered clinically significant. Therefore, if 60% of families in the core navigation condition engage in mental health services (estimates based on our prior work), to detect a 25% difference (i.e. 75% of families in any of the FN delivery conditions engage in services), and assuming 2-tailed tests and a type 1 error rate of 5%, approximately 304 participants are required to detect this effect (n=38 in each of 8 cells). Although 304 participants are required for our power analysis, we will be enrolling 715 human subjects which include 304 parent/legal guardian, 304 index children for primary analysis and around 107 siblings for families with more than one eligible child. Additional sibling analysis will be done to explore differences in service goals etc.

We expect strong effects of study mediators, in particular fidelity variables and variables that are central to our theoretical model, such as increased parent capacity. Following published guidance based on an empirical review, we estimate that our design will have at least 80% power to detect mediation effects where the paths from independent variable to mediator and from mediator to outcome are of at least small-to-medium effect (ES=.26). Given that our mediation analyses are designed to support decisions regarding intermediate outcomes to be tracked for quality control and assurance, effect sizes less than this magnitude are not considered to be clinically important. In contrast, analyses of patient-level treatment moderators are exploratory as we have no evidence to support hypotheses of any effect.

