**Objective 1: Effectiveness of FN delivery strategies.**

Following an intent-to-treat model, multiple regression models will be used to test hypotheses regarding the main effects of the three delivery strategies and their combined effects on the study's primary outcome, engagement in appropriate mental health services. A series of increasingly complex models will be constructed to address each specific index of outcome. For example, a logistic regression analysis will test receipt of behavioral health services within 90 days. Cox regression (proportional hazards) analyses will then be used to test the effect of each factor on time-to-scheduling date, and then on time-to-receipt of behavioral health services (with *time to third-next-available appointment* included as a covariate). Given that children may be referred to behavioral health services beyond those designated as primary in their initial visit, multi-level models will then be constructed with time-to-receipt of each behavioral health service as an outcome and with services clustered within child. Similarly, engagement in services will first be analyzed with logistic regression using our definition of engagement in care as a binary outcome, with subsequent multilevel models to analyze engagement in multiple services.

For outcomes involving engagement with services, sensitivity analyses will be conducted in which missing data from the EHR is interpreted as failure to engage in services. While we do not hypothesize interactions among the delivery strategies, these will also be explored. Following recommendations for factorial designs, effect coding (not dummy coding) will be used for experimental conditions to assess for interaction. In addition to evaluating effects "at the margins" using all available cells, results for each individual cell will also be reported, as will simple main effects.

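### The 90-day logistic model prespecifies no baseline covariate, although parent capacity and family resources are measured before randomisation, so some power per factor may be left unused

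*Combined protocol and SAP*

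**What the plan says.** Section 12.2 sizes the trial on 90-day receipt ("we powered our study on the dichotomous variable"). It supposes a reference rate ("if 60% of families in the core navigation condition engage in mental health services") and an improved rate ("75% of families in any of the FN delivery conditions engage in services"), a two-sided 5% test and 304 families. No power is stated for the main effects; 80% appears only for mediation.

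In section 12.3, Objective 1, "a logistic regression analysis will test receipt of behavioral health services within 90 days". No covariate is attached to that model. The only covariate named under Objective 1 is the time to the third-next-available appointment, in the Cox analysis. The overview of section 12.3 uses baseline characteristics to check balance, and Objective 2 uses the capacity and resource constructs as mediators.

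Section 8 says the literature backs the hypothesis that "initiation of behavioral health services is directly influenced by several key domains", and lists parents' motivation and capacity and families' resources among those domains. Table 2 schedules the parental attitudes inventory, the PHQ-2 and the Family Resource Scale at baseline; for the PHQ-2 the timing is "Baseline, 3, 6, 9, 12 months". Section 9 fixes the order: "The FP will administer the baseline assessment measures and then the family will be randomized".

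**The concern.** A covariate measured before randomisation cannot be affected by the assigned condition. If it predicts the outcome, including it in the model sharpens the test of each factor without enrolling anyone else. The plan itself argues that these domains influence the outcome and schedules their measurement at the right time, yet gives them no role in the model that tests the powered endpoint.

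Each main effect rests on about 80% power, and section 12.2 adds nothing for loss. The protocol summary says the results decide which components go forward to a later trial, so a missed effect could drop a useful delivery strategy. Naming the covariates in advance also removes the option of choosing them after the outcome data have been seen.

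**Working it through.** **1. Reproduce the plan's figure.** Inputs from section 12.2: p1 = 0.60, p2 = 0.75, difference 0.15, two-sided 5%. Power is assumed to be 80%. The pooled rate is 0.675.

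n per level = [1.960 × √(2 × 0.675 × 0.325) + 0.842 × √(0.60 × 0.40 + 0.75 × 0.25)]² / 0.15²
= [1.960 × 0.6624 + 0.842 × 0.6538]² / 0.0225
= (1.298 + 0.550)² / 0.0225 ≈ 151.9, so 152 per level and **304 in total**.

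This is an exact match. Power at 152 v 152 is 80.0%. Other two-sided versions do not match: 330 at 80% with continuity correction, 348 at 85% and 406 at 90%, both without it. The sizing is therefore an unadjusted comparison of two proportions. Sections 5 and 12.2 give conflicting cell counts, but the factor margin is 152 v 152 whenever 304 families split equally.

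**2. Analytic effect of adjustment.** If the baseline scores jointly explain a share R² of the outcome variance, the comparison behaves roughly as if it had 152/(1 − R²) families per level. Equivalently, about 304 × (1 − R²) families suffice for 80% power. The documents give no R², so the values below are assumptions.

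| Assumed R² | Power per factor | Families for 80% power |
|---|---|---|
| 0 | 80.0% | 304 |
| 0.05 | 82.0% | 289 |
| 0.0676 (correlation 0.26) | 82.7% | 283 |
| 0.10 | 84.0% | 274 |
| 0.15 | 86.0% | 258 |

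For the 0.26 row: 152/0.9324 = 163.0, and power = Φ[(0.15 × √163.0 − 1.298)/0.6538] = Φ(0.944) = 82.7%. An unpooled version agrees on the gain: z = 0.15/√(0.4275/152) = 2.828 gives Φ(2.828 − 1.960) = 80.7%, and z/√0.9324 = 2.929 gives Φ(0.969) = 83.4%, a gain of 2.6 points. The value 0.26 is borrowed from section 12.2, where it is the smallest mediation path of interest. Reading it as a baseline-outcome correlation is an assumption.

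**3. Simulation of the model itself.** Four effect-coded factors, 19 families in each of 16 conditions, one active factor with marginal rates 60% v 75%, a Wald test, and 6,000 replicates per row (simulation error about 0.5 points, √(0.8 × 0.2/6000)).

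| Assumed OR per SD of a composite baseline score | Mean R² | Unadjusted power | Adjusted power | Gain (points) |
|---|---|---|---|---|
| 1.0 | 0.003 | 80.0% | 80.0% | 0 |
| 1.25 | 0.013 | 80.6% | 80.9% | 0.3 |
| 1.5 | 0.035 | 81.4% | 82.7% | 1.3 |
| 2.0 | 0.085 | 80.6% | 84.2% | 3.6 |
| 2.5 | 0.131 | 81.2% | 86.4% | 5.2 |
| 3.0 | 0.169 | 80.0% | 86.9% | 6.9 |

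Two further scores with no predictive value cost 0.3 points or less in every row.

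**4. Effect on the odds ratio.** The marginal odds ratio is (0.75/0.25)/(0.60/0.40) = 2.0. With adjustment it becomes conditional: 2.14 when the score has an odds ratio of 2.0 per SD, and 2.34 at 3.0. An adjusted odds ratio therefore cannot be read directly against 60% v 75%; a standardised risk difference can.

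**The case against.** The strongest reply is that nothing is broken. The unadjusted test is valid, matches the sizing and estimates the marginal contrast directly. That stands in full.

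The plan is also silent on covariates; it does not exclude them. Section 12.3 speaks of multiple regression, offers the logistic model as an example and foresees models of growing complexity. That stands too. A reader might infer that the scores were deliberately left out, but the text shows only that none is prespecified for this test.

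A reader might further infer that the scores are strongly prognostic and the gain large; a combined correlation of 0.5, for instance, would put power near 90%. The documents do not support this. Section 8 states a hypothesis about broad domains and does not say how well a two-question depression screener or a resource scale predicts receipt by 90 days. The strong effects expected in section 12.2 concern mediators, such as an increase in parent capacity, not baseline levels. All families also receive core navigation, which section 8 says targets these same domains and which could weaken the baseline association.

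Availability is not secure for all three scores. The attitudes inventory is in Table 2 but absent from Appendix A and from the list of research measures in section 9, and its length is given as 21 items in the Objective 2b text and 26 in Table 2. PHQ-2 and family resources appear at baseline in both Table 2 and Appendix A.

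Finally, adding only theory-based scores would be selective while the minimisation variables (for example education, gender, race/ethnicity and screening score) are also unnamed in the model. This is fair, and the fix includes them.

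The objection that these constructs are mediators does not hold for baseline values: only post-randomisation values lie on the causal path.

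**Conclusion.** The point holds as a matter of efficiency. It is not a bias, and 304 is not an error. From about 80% power per factor, prespecified adjustment would add nothing if the scores are not prognostic, about 2 to 3 points at a combined correlation of 0.26, and up to about 7 points for strong scores.

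Three assumptions carry this: 80% is the intended power for main effects (inferred from the match to 304), each factor splits 152 v 152, and prognostic strength lies in the range shown, for which the documents offer no estimate. Because uninformative terms cost almost nothing, the change is worth making without knowing where in that range the truth lies.

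**What to change.** In section 12.3, Objective 1:

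- Prespecify baseline PHQ-2 and baseline Family Resource Scale scores as linear covariates in the effect-coded 90-day logistic model and in the Cox models, together with the minimisation variables, whose final list should be named.
- Reconcile Table 2 with the section 9 list and Appendix A on whether the attitudes inventory is collected at baseline. If it is, add its baseline score.
- Use pre-randomisation values only; keep later values of the same scales for Objective 2.
- Fill missing baseline scores by simple single imputation so that no family is dropped.
- Report each factor's effect as a covariate-standardised risk difference and risk ratio for 90-day receipt.

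The cost is a few lines of text and a few model terms. PHQ-2 and family resources are already scheduled at baseline. The small downside is that the odds ratio becomes conditional, which the standardised estimate resolves.

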## 4.2 Study Outcome Measures (See Table 1)

### 4.2.1 Primary Outcome Measures

#### Objective 1: To identify the most effective strategy to deliver FN

**Our primary outcome measure is receipt of behavioral health services within 90 days (yes/no)** will be defined as first encounter with behavioral health services within 90 days of randomization obtained from the electronic health record including Family Partner's template documentation.

Related to this primary objective, we will evaluate *time-to-receipt of behavioral health services* defined as time from randomization to first behavioral health service encounter obtained from the electronic health record, including family partner's template documentation. Dates will be obtained from administrative and billing data (electronic health records) for services within DotHouse, and FP documentation for services outside the health center.

A second primary outcome includes change in child symptoms over time.

- Pediatric Symptom Checklist-17 (PSC-17). A 17-item psychosocial screen designed to recognize cognitive, emotional, and behavioral problems. Three subscale Internalizing, Attention, and Externalizing have specific cutoffs and provide additional guidance regarding need for further follow-up. PSC-17 is embedded in the Epic (electronic health record) as a self-scoring form. It is widely used and has been validated in diverse populations.
- The Survey of Wellbeing of Young Children (SWYC). The SWYC screens for cognitive, motor, language, and social-emotional development among children up to 5½ years of age. We will track behavioral symptoms using the SWYC's Preschool Pediatric Symptom Checklist (PPSC), an 18-item questionnaire that has demonstrated strong concurrent validity with the Child Behavior Checklist (CBCL) and parents' reports of socio-emotional diagnoses as well as acceptability in diverse populations. Translations are available in a range of languages and the SWYC is currently being incorporated into the Epic system used at DotHouse.

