**Table 1. Primary and Secondary Outcomes**

	Outcome	Description	Measurement Source	Timing
Primary	Time to services	Time from randomization to first behavioral health service encounter	Electronic health record including FP's template documentation	90 days
	Access to services	1 st encounter with behavioral health services within 90 days of randomization	Electronic health record including FP's template documentation	90 days
	Child symptoms	Score on PSC-17 and SWYC	Measures will be sent to families via Epic's mobile app MyChart or administered by Zoom/telephone in REDCap or sent to the parent by mail	Baseline 3, 6, 9, & 12 mo
Secondary	Retention in services	≥4 visits or resolution of service need for families receiving psychotherapeutic or psychopharmacological services	Electronic health record including FP's template documentation	90 days
	Patient Satisfaction	HCQ & PSN-I	Measures will be sent to families via Epic's mobile app MyChart or administered by Zoom/ telephone in REDCap or sent by mail	6 mo
	Qualitative Parent Interviews	Parent interviews to describe the effect of cultural and linguistic concordance between patients and FN.	Interview completed through Zoom/phone and audio recorded, stored in HIPPA compliant BOX drive.	6 mo
	Qualitative DotHouse Staff Interviews	DotHouse staff interviews to understand their perspective in the implementation of family navigation (work flow changes etc).	Interview completed through Zoom/phone and audio recorded, stored in HIPPA compliant BOX drive.	ongoing

Note: The PSC-17 is currently administered to children at pediatric well visits at DotHouse as part of usual care. Plans are to implement the SWYC in summer/fall of 2018. Both tools have been used extensively and research supports use for symptom monitoring.

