**Strategy C: Pediatric Surveillance v. Enhanced: Tracking at 3, 6, 9, and 12 months.** In core FN (i.e. Pediatric Surveillance at well-child visits), monitoring is determined by standard pediatric practice. In Massachusetts, behavioral screening is mandated at every pediatric visit, which for children in the target population (ages 3-12 years) is annually. In experimental conditions with "enhanced monitoring," FPs will screen children using validated instruments quarterly (SWYC, PSC-17 based on age) and communicate results to the child's care team. The screening tools will be deployed through MyChart , the EPIC EHR patient portal. Results feed directly into the child's record. Screening tools may also be deployed through REDCap or mailed to the parent in a sealed envelope with a stamped and addressed return envelope inside. Once the mailed parent measures are received by research staff at Boston Medical Center, they will be manually entered into RedCap and the paper copies will be stored in a locked filing cabinet in a locked office. The FP will be responsible for initiating and tracking the screening. She will message the child's PCP when new screening results are available and communicate with the PCP and care team regarding any changes in symptoms. We expect additional costs of increased monitoring to be modest, and that the additional information will allow care to be better aligned with children's symptomatology and, thus, lead to improved engagement with services.

**Strategy D: tailored vs standardized, schedule-based visits with families.** Families who receive tailored visits, will work with their FN on addressing issues as they arise. They will not have any pre-specified schedule for visits or contacts. Families who received standardized scheduled visits, will have a pre-specified schedule of visits. This will include monthly contacts with families for 6 months. Each contact will have a specified agenda which includes review of family goals, and a topic (e.g. what is an individualized education plan) to review.

Regardless of the combination of delivery components to which families are randomized (core or enhanced strategies), families will core FN elements.

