**Development of a service plan.** In consultation with the primary care team and the pediatric integrated behavioral health clinician, the family partner will work with the family to collaboratively choose from a selection of referral options: onsite integrated behavioral health services with a clinician embedded in primary care pediatrics; onsite behavioral health services provided in the behavioral health department; school based services; and/or referral to an external behavioral health clinician or agency.

**Ensuring linkage with service.** The family will receive assistance with referral and coordination of care based on the child’s needs and the family’s interest. The FP will ensure that a referral is made, an appointment scheduled, support family engagement in services through such activities as text reminders and assistance with transportation.

**Ongoing engagement with FP.** Families’ ongoing engagement with the FP will be guided by the core components of FN described above, family needs, and the study condition to which they were assigned. For example, some families will meet with the FP in the community, others will only do so by phone or in the clinic; some may use Act.MD to assist with care coordination with school or conduct remote visits, others will not have access to this technology. Based on our previous experience, we expect considerable variation in the intensity of engagement among families. The FP will have a manualized intervention workbook that will help guide their interaction with families. The FP will document all FN activities and contacts in a FN log within the EHR. We expect that the range of ongoing activities might include assistance in obtain school evaluations and necessary accommodations (504B plan, IEP); linkage to community-based supports such as parent groups and recreational activities; trouble shooting challenges to accessing services; and coordinating services between primary care, school, and specialty services. The Family Partner will also complete a Family Needs worksheet that will be used to summarize the amount of support required by a family. This worksheet will not be administered to participants but may be used as process data by the research team.

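### The per-service time-to-receipt model has no stated clock start or risk set for services referred after randomization; if the first-encounter definition is carried over, differences in referral timing appear as differences in speed

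*Combined protocol and SAP*

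**What the plan says.** Time-to-receipt is defined once. Section 4.2.1 has it "defined as time from randomization to first behavioral health service encounter", and Table 1 repeats this ("Time from randomization to first behavioral health service encounter") with a timing of 90 days.

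Section 12.3, Objective 1, under an intent-to-treat heading, starts with child-level models: logistic regression for receipt within 90 days, then Cox regression. It then notes that "children may be referred to behavioral health services beyond those designated as primary in their initial visit" and, for that reason, adds a further stage in which "multi-level models will then be constructed with time-to-receipt of each behavioral health service as an outcome and with services clustered within child". A multilevel model of engagement in multiple services follows. For neither stage does the plan say when a service becomes a row, and for the time-to-receipt stage it does not say when the clock starts or when follow-up is censored.

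On the order of events, section 9 says "Before initiation of FN, FPs will assign each family an experimental condition using a computer program". In the service-plan step that it describes next, "the family partner will work with the family to collaboratively choose from a selection of referral options". Under Strategy C (section 8), at the enhanced level, "FPs will screen children using validated instruments quarterly (SWYC, PSC-17 based on age) and communicate results to the child's care team".

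**The concern.** A service becomes a row only if it is referred. Which services are referred, how many and when can be settled after assignment, with the Family Partner whose way of working is the randomized factor. The protocol gives reasons why this might differ by level: quarterly screening results under C, attendance at school meetings under B, monthly agenda-based contacts under the standardized level of D. The set of rows may therefore itself be a result of treatment.

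If the clock for every row starts at randomization, a service first referred in month 5 is treated as at risk, and as not yet received, for five months in which it could not have been received. A component that uncovers additional needs during follow-up would then look slow. The trial exists to choose components for an optimized model, so a misleading adverse hazard ratio could weigh against a useful one.

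**Working it through.** **1. The plan's own figure.** With 60% v 75%, two-sided 5% and 80% power (power for the main effect is not stated; 80% is assumed), the pooled proportion is 0.675 and

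n per level = [1.960 × √(2 × 0.675 × 0.325) + 0.842 × √(0.60 × 0.40 + 0.75 × 0.25)]² / 0.15² = (1.298 + 0.550)² / 0.0225 ≈ 152.

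That gives 304 in total, as in section 12.2. It rests on the child-level 90-day outcome and does not depend on the per-service model.

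**2. Inputs for the per-service check.** From the documents: 304 index children, so 152 per factor level; 12 months of EHR follow-up (365 days); 60% receipt by day 90, taken as the referral-to-receipt rate. With exponential waits the daily rate is −ln(0.40)/90 = 0.01018. Assumed, because the documents give nothing: one referral per child at day 0, plus a Poisson number of extra referrals spread evenly over a window. The plan does not name the form of the multilevel model; a Cox model on service rows was used because it follows the Cox stage. It was fitted without a child random effect.

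**3. Hand check of the mechanism.** Take 0.3 v 0.6 extra referrals per child over days 0 to 180, with identical waits from referral.
- A day-0 row is received by day 90 with probability 0.60.
- An extra row is received by day 90 with probability (90 − 0.60/0.01018)/180 = (90 − 58.9)/180 = 0.173.
- Share of rows received by day 90: (0.60 + 0.3 × 0.173)/1.3 = 0.50 v (0.60 + 0.6 × 0.173)/1.6 = 0.44.

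The second level looks slower only because more of its rows started late. If all extra referrals fall on day 0, both shares are 0.60.

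**4. Simulation, 2,000 trials per scenario, true per-service hazard ratio 1.00.**

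| Extra referrals per child, and window | HR, clock from randomization | HR, clock from referral |
|---|---|---|
| 0.3 v 0.3, days 0–180 | 1.00 | 1.00 |
| 0.3 v 0.6, days 0–180 | 0.89 | 1.00 |
| 0.3 v 0.6, days 0–180, children differ in underlying rate | 0.92 | 1.00 |
| 0.3 v 0.6, referrals and follow-up within 90 days | 0.90 | 1.01 |
| 0.3 v 0.9, days 0–180 | 0.83 | 1.00 |
| 0.3 v 0.6, days 0–365 | 0.82 | 1.00 |
| 0.5 v 0.5, days 0–90 v 90–270 (later) | 0.67 | 1.00 |
| 0.5 v 0.5, days 0–180 v 0–60 (earlier) | 1.22 | 1.00 |
| 0.3 v 0.9, all at day 0 | 1.00 | 1.00 |

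Delayed entry at referral, keeping the clock from randomization, gives 1.00 to 1.01, or 1.02 where children differ in underlying rate.

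In the second row the median time to receipt per service is 90 v 106 days, while the child-level first-encounter hazard ratio is 1.07: the two analyses point in opposite directions.

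**5. When there is a real effect.** With 0.3 v 0.8 extra referrals over days 30 to 180, a true 1.00 is estimated as 0.82 and a true 1.30 as 1.01. With 0.3 v 0.5, a true 1.00 becomes 0.91. Starting the clock at referral returns 1.00 and 1.30.

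**6. Clustering.** Grouping rows within child allows for correlation among a child's services. It does not remove the days before referral from a row's time at risk, and it does not make the set of rows independent of assignment. This step is reasoning; no random-effect model was fitted.

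**The case against.** The strongest reply is that this is missing detail in a follow-on model. Section 12.3 does not say that each service's clock starts at randomization. That origin is stated for the first encounter only, and a referral-date clock is compatible with the text, the more so as section 11.2 lists referrals made and completed among the abstracted EHR data. This stands: the randomization origin for later services is an inference. But it is the only definition of the term in the plan, and an analyst who follows it gets the distorted answer.

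Nor does the plan say that the additional services are referred late. Appendix A marks referral to behavioral health at baseline only, and section 8 has the Family Partner working after the clinician's referral. This too stands in part. Yet section 9 has options chosen with the Family Partner after assignment, and navigation continues for up to 12 months, so later referrals remain possible.

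If Table 1's 90-day timing also carries over, a month-5 referral lies outside the window. The effect shrinks but does not vanish: 0.90 in the 90-day scenario.

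The referral counts are assumptions. That stands without reservation.

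A reader might also infer that generating more referrals is penalized in itself, or that enhanced levels always look slower. Neither follows: extra referrals at day 0 leave the hazard ratio at 1.00, and earlier referrals move it to 1.22.

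**Conclusion.** The point holds for the follow-on per-service model. Its rows can be selected after randomization by the process under test, and the plan supplies no origin, risk-set entry or censoring rule for them. If the only stated definition is applied, the hazard ratio for a strategy with more and later referrals is about 0.82 to 0.92 when the truth is 1.00, and 0.67 in an extreme case of later timing alone. These sizes depend on assumed referral numbers and timing, exponential waits and a Cox model; the direction depends on whether the strategy makes referrals later or earlier. Even with the clock at referral, the comparison is not intent-to-treat, because the rows are still chosen after assignment.

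Two stronger readings are not supported. The main results are not compromised: the 90-day outcome and the first-encounter Cox model use every randomized child with a fixed origin, and 304 reproduces without this model. And the multilevel model of engagement in multiple services does not share the clock bias, since engagement is a binary outcome there; it shares only the selection of rows.

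**What to change.** In section 12.3, Objective 1:

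- Start each service's clock at its referral date, or keep the clock from randomization with delayed entry at referral, and state the censoring rule.
- Label the per-service result descriptive because its rows are selected after randomization, and report referrals per child and time to referral by factor level beside it.
- Keep the child-level first-encounter analysis as the randomized comparison. If a randomized comparison over all services is wanted, use every index child as the unit, for example the number of distinct services received. That measures volume and not speed, and the text should say so.
- Label the multilevel model of engagement in multiple services descriptive for the same row-selection reason.

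The cost is SAP wording. Section 11.2 already lists referrals made and completed, and Family Partner templates that record referrals and attended appointments; the team should confirm that the extract carries a date for each. The downside is small: the per-service model no longer supports a causal claim about the components.
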